3. BACKGROUND AND RATIONALE

3.1 Background and Rationale

Antibiotic resistance is increasingly a major public health problem worldwide while the number of novel antimicrobial agents is decreasing. There is a clear association between antibiotic use and resistance rates at community as well as at patient-level [10, 11]. Reducing inappropriate use is essential to decrease antibiotic resistance and adverse events. The highest volume of antibiotic prescription occurs in the outpatient setting where antibiotics are most commonly prescribed for ARIs [1, 2]. So far, antibiotic stewardship programmes have mainly been developed and recommended for hospitals [2].

LRTIs are one of the commonest acute reasons to consult and are usually initially managed by GPs [3]. LRTIs include acute bronchitis, exacerbation of COPD and CAP. On the one hand, CAP is usually of bacterial origin, has a high morbidity and mortality rate and needs to be treated with an antibiotic [12]. On the other hand, in GPs practices, only 5-12% of patients presenting with LRTI symptoms have CAP and thus benefit from antibiotics [3, 4].

At primary care level, it is a challenge for physicians to identify amongst patients with LRTI, patients with CAP. There are no specific signs and symptoms enabling to identify with certainty patients with CAP. Definite CAP diagnosis is thus supported by the presence of a chest X-ray (CXR) infiltrate that is likely to be new [5]. The use of CXR has several limitations.

First, it is not always readily available at the GP level. In a recent German study, GPs performed a CXR in only 4.3% of patients with ARI and in a Swiss trial, 75% of patients with a diagnosis of CAP benefited from a chest X-ray [13, 14]. Second, its accuracy is limited. The accuracy of CXR (when compared to chest CT scan) has been estimated at 75% for detecting lung consolidation [15], and the overall sensitivity for the diagnosis of CAP has been estimated at 77%, with a 91% specificity [16]. Third, it exposes patients to radiation.

Chest CT scan, considered the gold standard imaging approach for pneumonia, cannot be used to routinely diagnose pneumonia because of its high cost, radiation dose and limited availability. Although chest magnetic resonance imaging (MRI) has a high sensitivity (93.8%) and specificity (97.8%) when compared to CT for the diagnosis of CAP in outpatients with LRTI [17], it is an expensive imaging solution and is not readily available.

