A meta-analysis of studies evaluating PCT to initiate or discontinue antibiotics in ARIs (14 trials with 4221 participants) showed that the use of PCT significantly reduced antibiotic treatment (84% with standard care versus 64% using PCT) in patients with ARI without affecting the treatment outcome [22].

The ProHOSP trial, performed in emergency departments of six hospitals in Switzerland, showed that patients with mostly severe LRTIs, a PCT guided approach to antibiotic prescription led to a diminished proportion of antibiotic prescription without increasing a composite adverse outcome measure (death, intensive care unit admission, complications and recurrent infections), suggesting that such an approach is safe [23].

Two studies conducted in GPs practices and including indistinctly patients with ARIs and LRTIs and showed that PCT guidance led to diminished antibiotic consumption without an increase in adverse outcomes.

In a Swiss trial, primary care physicians recruited 458 patients with ARI who, in the physician's opinion, were in need for antibiotics. They were randomly assigned to either a PCT-guided approach or to standard care. The proportion of antibiotic prescription was 97% with standard care compared to 25% with PCT-guided therapy. LRTIs were present in 47.6% and radiological pneumonia in 15% of the patients. Safety outcomes were similar in the PCT guided approach and standard care [24].

In a German trial, GPs recruited 550 patients with ARIs who were randomly assigned to PCT-guided

therapy or usual care. The proportion of antibiotic prescription was 36.7% in the usual care group compared to 21.5% after PCT measurement with no repercussions on patient safety [13]. However, only 36% of these patients had an LRTI and only 4.3% had a CXR performed, not allowing for calculation of the prevalence of radiological pneumonia.

PCT can then be used safely to decide on antibiotic prescription in patients with ARIs. However, its relatively low specificity to differentiate between viral and bacterial aetiology makes it a suboptimal tool particularly in setting with higher rate of viral infections, such as GPs practices. Data are needed to confirm the impact of PCT-guided therapy on antibiotic prescription rates compared to routine setting among patients with LRTIs in GPs practices.

Lung ultrasound is a sensitive and specific tool to detect lung infiltrates and identify patients with CAP and might compensate for the lack of specificity of PCT.

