5.2 Randomized Intervention Study

Primary outcome

Proportion of patients prescribed an antibiotic in each arm by day 28.

The following information will be collected to assess the proportion of patients prescribed an antibiotic in each arm by day 28:

- Day of the antibiotic prescription
- Antibiotic substance prescribed
- Dosage of antibiotic prescribed
- Duration of the antibiotic treatment prescribed

Secondary Outcomes

Clinical outcomes

- a. Duration of the episode: number of days during which the patient was symptomatic (defined by the daily symptom diary and telephone follow-up) within 28 days of follow-up.
- b. Duration of restricted daily activities: number of days during which the patient's daily activities (work or recreation) were restricted due to a respiratory tract infection.
- c. Clinical failure by day 7:
 - i. Admission to hospital within 7 days of follow-up
 - ii. Death within 7 days of follow-up
 - iii. No amelioration or worsening of relevant symptoms (fever and/or dyspnoea) at day 7
- d. Number of medical visits for the episode of LRTI within 28 days of enrolment.
- e. Serious adverse outcome: measured by day 28, based on the advent of at least one of the following events:
 - i. Death
 - ii. Secondary admission to hospital for any reason
 - iii. Complications (persistence of pneumonia, lung abscess, lung effusion, empyema or sepsis)
- f. Number of days with side effects related to antibiotics within 28 days of follow-up

The following information will be collected during telephone follow-up and recorded in the eCRF. It will also be obtained from the patient's diary.

Consultation process

- a. Median duration of time spent for the medical consultation, blood sampling, PCT measurement, lung US and total time spent in the practice.
- b. Quality of the ultrasound images. Agreement between GPs and experts on ultrasound images interpretation.
- c. Evaluation of the satisfaction of providers and of patients.

Economic aspects

- a. Cost / effectiveness ratio expressed as amount of money required per 1% absolute decrease of the proportion of antibiotic prescription.

Exploratory Outcomes

- a. Prevalence of different respiratory pathogens assessed by multiplex rt-PCR on nasopharyngeal swab and sputum
- b. Sensitivity and specificity of combinations of host biomarkers and gene expression signatures in identifying patients with serious adverse outcome, clinical failure or with pneumonia

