Naso-pharyngeal swabs will be systematically collected for further exploratory analysis. Sputum will also be collected if the patient is able to produce it. Venous blood samples will not be collected as blood drawing will not be systematically performed in these patients.

[figure not shown]

Figure 3: Description of the different arms of the study

Packaging, Labelling and Supply (re-supply)

Not applicable

Storage Conditions

Not applicable

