Transcripts will be read to identify abstract themes relating to the meaning of the text. After the identification of the main themes, these will be developed in a coding scheme that will be applied to the text. The codes will then be applied to the text of in an independent fashion by two different investigators. Software designed for qualitative analysis (QDA Miner[©] or Atlas.ti[©]) will be used.

Quantitative data

Quantitative data relating to the study processes will be obtained by questionnaires designed to assess different steps of the study process.

Clinical data will be collected as per protocol for the randomized trial

Randomized trial

All study participants will undergo clinical and laboratory evaluation at inclusion (Day 0) according to the arm to which they are allocated. The following data will be collected:

Clinical data collection

A short electronic case report form (eCRF) will be filled by the GP on a tablet computer provided by the study team. Data collected include demographic characteristics, medical history, symptoms and clinical examination findings. Whether or not the GP ordered supplementary tests for the management of the patient outside the scope the algorithm will be recorded.

Ultrasonographic (UltraPro arm) data collection

All US images captured will be digitally recorded and transferred via a secured internet connection along with relevant metadata to a secure server. For study quality control purposes, the quality of the image and the interpretation of a random sample of images will be evaluated retrospectively by an experienced radiologist.

Laboratory specimen collection

Blood samples

In the UltraPro and PCT arms, a total of 17.5 mL of whole venous blood will be drawn to perform the PCT POCT measurement and for the exploratory objectives.

50 µL of whole blood will be used for the POCT PCT measurement. The rest of the sample will be used for identification of novel host biomarkers and genetic (identification of SNPs in genes that regulate microvascular integrity and transcriptomics) analyses that will be done in batch after the completion of the study. This will be performed at the Sandra Rotman Laboratory in Ontario, Canada

The following table describes the nature of the biological sampling:

Tube	Volume	Storage	Aim
EDTA 7.5 ml	20µL of whole blood	None	POCT PCT measurement
	3 x 1000 µL of whole blood	-80°C	SNPs analysis Biobank
EDTA 7.5 ml	3 x 1000 µL of plasma	-80°C	Novel host biomarkers Biobank

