11.2 Determination of Sample Size

The sample size was calculated to assess a decrease in antibiotic prescription of at least 15% between the UltraPro and the PCT arms as well as 15% between the PCT arm and usual care.

The proportion of patients receiving antibiotics with the usual care is estimated to be around 60% and to decrease to 45% using PCT and to 30% combining PCT and ultrasound. These numbers have been extrapolated from the subgroup of patients with LRTI in a study at primary care level in the Netherlands [3].

A study sample of 14 GPs and 15 patients per GP in each arm (210 patients per arm and a total of 630 patients) gives a power of 80% to detect a decrease in antibiotic prescription from 60% (usual care) to 45% (PCT), and from 45% (PCT) to 30% (UltraPro), with 5% level of significance, when adjusting for clustering at practice level (intracluster coefficient 0.06) [3]. This sample size guarantees a power of 80% to prove non-inferiority in terms of duration of activities restriction (non-inferiority margin=1 day, standard deviation=4 days) as well as of composite adverse outcome (probability in the “usual care” arm 0.05 with a non-inferiority margin of 0.02). Simulations used to determine the sample size are shown in the following figures.

[figure not shown]

Figure 4: Statistical simulations used to determine sample size

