 - combined biomarkers based on sensitivity and specificity generated by classification and regression trees (CART) analyses, to predict the development of a life-threatening disease, clinical failure, or the presence of pneumonia (using a clinical diagnosis).

For each arm of the study, socio-demographic and clinical characteristics will also be described.

Interim analyses

For quality and safety purposes, interim analyses will be performed after inclusion of 50 patients in each of the intervention and control arms. The results of the interim analysis will be reviewed by the steering committee.

Safety analysis

An annual safety analysis will be done by the study coordinator, comparing the incidence of clinical failure by day 7, hospital admissions and deaths between both groups. This will be included in the annual safety report.

Adverse events will be reported to the steering committee within seven days.

Deviation(s) from the original statistical plan

Any deviation from the original statistical plan will be justified and reported in the final study report.

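### Section 11.4 gives no validation for the CART combined-biomarker analysis, so accuracy read from the fitted tree would be optimistic

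*Combined protocol and SAP*

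**What the plan says.** Section 11.4, Secondary Analyses, ends with diagnostic performance. Individual markers are assessed by likelihood ratios and ROC area. For marker combinations the plan is one line: "combined biomarkers based on sensitivity and specificity generated by classification and regression trees (CART) analyses". The targets are life-threatening disease, clinical failure and clinically diagnosed pneumonia. The synopsis (Statistical Considerations) repeats the line, with serious adverse outcome in place of life-threatening disease.

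Section 5.2 makes this an exploratory outcome and widens the inputs: "Sensitivity and specificity of combinations of host biomarkers and gene expression signatures".

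Marker blood is limited to two arms. Section 8.5 states: "In the UltraPro and PCT arms, a total of 17.5 mL of whole venous blood will be drawn". For usual care, Section 8.1 states: "Venous blood samples will not be collected as blood drawing will not be systematically performed in these patients". Section 8.5 adds that the marker and genetic assays are run in batch after the study ends.

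The documents give no candidate marker list, class weights or priors, minimum node size, pruning rule, or internal or external validation for this analysis. Where they mention validation, it concerns the PCT device, the symptom diary or data checks.

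**The concern.** A classification tree searches over markers and cut-points for the splits that best separate cases from non-cases in the data at hand. If its accuracy is then read from those same patients, part of the apparent accuracy comes from the search itself. The optimism grows with the number of candidate inputs and shrinks with the number of cases. Here the cases are probably few, and the inputs may include gene-expression data.

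At stake is the credibility of the combined-marker result. Section 3.1 presents additional biomarkers as a possible way to reduce antibiotic use further, so an accuracy figure inflated by overfitting could be carried forward as a promising signature.

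**Working it through.** The documents give no expected sensitivity, specificity, case count or marker count for this analysis, so there is no figure of theirs to reproduce. The check has two parts.

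**1. How many cases are available**

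- Patients with marker blood: 2 arms x 210 (Section 11.2) = 420.
- Pneumonia: Section 3.1 says "only 5-12% of patients presenting with LRTI symptoms have CAP". This gives 0.05 x 420 = 21 to 0.12 x 420 = 50.4, or about 50.
- A higher rate in the same section comes from a Swiss primary-care trial of acute respiratory infection: "LRTIs were present in 47.6% and radiological pneumonia in 15% of the patients". This gives 0.15 x 420 = 63.
- Composite adverse outcome: Section 11.2 plans on 0.05 in usual care. If that rate also holds in the two intervention arms, 0.05 x 420 = 21.
- Clinical failure: the documents give no planning rate, so no count can be derived.

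**2. What a fitted tree shows when the markers carry no information**

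Simulation settings: 420 patients, ten independent standard normal markers unrelated to outcome, 21 or 50 cases, Gini trees, 150-200 replicates per setting. Ten-fold cross-validation was run on 60 replicates per setting for the scikit-learn trees. The number of markers and all tree settings are assumptions.

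The true answer is known. If markers are independent of outcome, a tree flags new cases and new non-cases with the same probability p. Sensitivity is then p, specificity is 1 - p, and their sum is 1.

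Entries are sensitivity/specificity.

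| Tree | 21 cases, apparent | 21 cases, cross-validated | 50 cases, apparent | 50 cases, cross-validated |
|---|---|---|---|---|
| Weighted, depth 3 | 0.92/0.64 | 0.38/0.61 | 0.82/0.54 | 0.51/0.51 |
| Weighted, depth 3, minimum leaf 10 | 0.93/0.60 | 0.41/0.57 | 0.83/0.52 | 0.52/0.49 |
| Weighted, depth 4, minimum leaf 10 | 0.96/0.67 | 0.36/0.65 | 0.87/0.57 | 0.45/0.53 |
| Weighted, minimum leaf 20 | 0.91/0.78 | 0.27/0.75 | 0.87/0.69 | 0.38/0.62 |
| Weighted, minimum leaf 7 (larger tree) | 1.00/0.87 | 0.18/0.82 | 0.96/0.78 | 0.31/0.69 |
| Equal priors, rpart, pruned at minimum cross-validated error | 0.91/0.71 | not run | 0.85/0.65 | not run |
| Unweighted, rpart defaults | 0.04/1.00 | not run | 0.15/0.99 | not run |
| Unweighted, rpart, pruned as above | 0.00/1.00 | not run | 0.00/1.00 | not run |
| Unweighted, fully grown | 1.00/1.00 | 0.07/0.94 | 1.00/1.00 | 0.14/0.86 |

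A separately coded tree at weighted depth 3 and 50 cases gave apparent sensitivity as low as 0.80, hence the lower end of 80-96% for moderate weighted trees. A repeat of unweighted rpart defaults at 50 cases gave up to 0.19.

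Taking sensitivity + specificity - 1 for the weighted tree with minimum leaf 20:

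- 21 cases: apparent 0.91 + 0.78 - 1 = 0.69; cross-validated 0.27 + 0.75 - 1 = 0.02.
- 50 cases: apparent 0.87 + 0.69 - 1 = 0.56; cross-validated 0.38 + 0.62 - 1 = 0.00.
- 63 cases: apparent 0.84 + 0.68 - 1 = 0.52; cross-validated 0.39 + 0.61 - 1 = 0.00.

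Across the weighted trees in the table, the apparent value runs from 0.83 + 0.52 - 1 = 0.35 to 1.00 + 0.87 - 1 = 0.87, against a true value of 0.

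The pruned equal-priors row matters most. Choosing tree size by cross-validation does not remove the optimism if sensitivity and specificity are still read from the training patients.

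**The case against.** The strongest reply is that the plan does not say accuracy will be read from the training patients. That is correct. A reader might infer from the wording that resubstitution accuracy is what will be reported, but the documents are silent on which patients are used for evaluation. The point is that nothing in the plan prevents it, and that accuracy generated by the trees is most naturally read that way.

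A reader might also take one figure, such as apparent sensitivity near 90%, as the expected bias. The documents do not support that. The figure needs class weighting and a moderate tree size, and neither is specified. Unweighted default trees give 4-19%, and unweighted trees pruned by cross-validation keep almost no split, which is the right answer for noise. Sensitivity also means little without its specificity, which was 52-78% for the moderate weighted trees.

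The case counts can be challenged as well. The 5-12% is a background rate for patients with LRTI symptoms. Section 7.2 requires acute cough plus at least one further sign or symptom, and pneumonia is by clinical diagnosis, so the true count may be higher. Clinical failure, a further target, may be commoner. More cases reduce the optimism but do not remove it, as the 63-case run shows.

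Finally, the outcome is exploratory and individual markers are assessed separately. It would go too far to say that the trial could not tell a useful marker set from noise. These replies limit the importance of the point. They do not supply the missing validation.

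**Conclusion.** The point holds as a gap in the plan: no validation or optimism correction is specified for the CART analysis, and accuracy taken from the fitted tree would be biased upwards. The figure of 420 patients follows directly from the documents. The 21 to 50 pneumonia cases (63 at 15%) and about 21 adverse outcomes rest on assumed rates. The simulated values are illustrative. For ten noise markers, moderate weighted trees show apparent sensitivity of about 80-96% with specificity of about 52-78%. The larger weighted tree in the table reaches 96-100% with 78-87%, and unweighted trees span 0% to 100% apparent sensitivity. The direction of the bias is clear, but its size cannot be fixed without settings the plan does not give. Gene-expression inputs were not simulated. The primary and secondary clinical comparisons are unaffected, so the priority is low.

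**What to change.** In Section 11.4, and in the matching synopsis line, state that:

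- CART sensitivity and specificity will be reported as cross-validated or bootstrap optimism-corrected values, with confidence intervals;
- marker selection, tree growing and pruning will all be repeated inside each resample;
- resampling will be by GP where case numbers allow;
- apparent values will be shown only alongside the corrected ones.

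It would help to list the candidate markers and the tree settings (weights or priors, minimum node size, pruning rule) at the same time, since the results above turn on them.

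The qualification on GP resampling is needed. There are 2 x 14 = 28 GPs in the two arms, so 21 cases average 21/28 = 0.75 per GP, and ten folds would hold about two cases each, possibly none in some. Bootstrap by GP, or pooling predictions over folds before computing accuracy, are workable alternatives. The simulations did not include GP clustering, so they do not show how much this refinement matters.

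The cost is a few lines of analysis code and lower reported accuracy. No extra patients, samples or visits are needed. Because the assays are run after study completion, the rule can be fixed before any marker data exist.

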11.5 Handling of missing data and drop-outs

Any missing data at the enrolment visit due to incomplete completion of the pre-assigned components of the algorithm will lead to the patient being assigned to the intention to treat analysis. We expect that the use of electronic CRFs using tablet computers will keep these to a minimum.

We expect some loss of patients to follow-up if they are not successfully contacted for follow-up by telephone. All efforts will be made to be made to keep these to a minimum. During follow-up, calls we will also remind patients to fill the self assessment by daily diary.

12. QUALITY ASSURANCE AND CONTROL

The PI is responsible for proper training of all involved study personnel (who will all hold a “GCP for Investigators and Sub-investigators” official accreditation) and for implementing and maintaining quality assurance and quality control systems with written standard operating procedure and working instructions.

He will prepare and maintain adequate and accurate source documents designed to record all observations and other pertinent data for each subject enrolled into the study

12.1 Data handling and record keeping / archiving

Case Report Forms

The data collected by the GPs and by the study team will be entered directly in an eCRF on a tablet computer provided by the study and using a secure web-based electronic data capturing solution, (REDCap®). The web-based data capture tool uses real-time error, range and consistency checks and data are transferred to the central database on a daily basis. PCT and ultrasound results will also be entered directly in the eCRF.

Patient diary

Patients will be able, if the wish to, to fill in the symptoms diary using a secure online server hosted on our REDCap® servers. Electronic diaries will be kept following the same practices as the case report forms.

Specification of source documents

Source documents (forms recording eligibility criteria, informed consent forms) will be kept in the GP practice and stored according to specific regulation.

Record keeping / archiving

All study data will be archived for a minimum of 10 years after study termination or premature termination of the clinical trial. Electronic data will be stored at the Lausanne University Hospital server. Paper study data (apart from source medical files which will remain in the GP's practice and stored according to specific regulation) will be stored at the Infectious Diseases Service in Lausanne for a period of ten years under the responsibility of the principal investigator.

